# Adverse Events Expected with Resiguimod application at the vaccine site.

The investigator brochure specifies the following adverse events in more than 1800 patients treated with topical resiquimod in 25 clinical studies. Reported adverse events were primarily local adverse events including protocol-defined local skin reactions (including, erythema, edema, ulceration, vesicles, weeping, scabbing, and flaking); and protocol-defined local symptoms at the site of administration (including pain, burning, pruritus, and numbness/tingling). Other adverse events at the application site include drainage, infection, and pigmentation changes. Systemic adverse events that may be related to resiquimod due to a systemic induction of cytokines and/or release of locally induced cytokines into the circulation include influenza-like symptoms (e.g., fever, headache, arthralgia, myalgia, chills, asthenia, fatigue), and transient decreases in neutrophils and total leukocytes that may be related to cellular trafficking to the application site. Other infrequent adverse events that were considered possibly or probably related to study medication included liver function test abnormalities, abdominal cramping, nausea, vomiting, diarrhea, backache, neck pain, rhinitis, urticaria, and dizziness.

The formal list, below, of expected AEs for resiquimod, for this study, is based on published data related to its clinical use 65;66 The table below is based on a study applying resiquimod 3 times per week for 4 weeks, for treatment of actinic keratosis. This study had 4 treatment arms, using 0.01, 0.03, 0.06, and 0.1% resiquimod gel. We will be using 0.2% resiquimod gel, only once a week; so toxicities from 3x/weekly administration with 0.06% resiquimod use may exceed what we observe65. Overall in that study, no deaths or serious adverse events were reported, but some adverse events are described as severe. We expect grade 2 toxicities in these categories. Listed in the table below are those categories where adverse events were recorded in 10% of patients or more, in any study group, but the percentages listed are those for patients receiving resiquimod 0.06% three times per week.

Table 8: Toxicity Data for Resiquimod Grade 2:

CTCAE Category	Description	Percent with possibly or probably related AEs at 0.6% resiquimod three times per week
	Application site burning	25%
	Application site	6%
General disorders and administration site	erythema	
	Application site pain	16%
conditions	Application site pruritus	25%
	Application site reaction	None
	Fatigue	9%
	Rigors/chills	16%
Musculoskeletal and connective tissue disorders	Arthralgia	16%
Wusculoskeletal and connective tissue disorders	Myalgia	6%
Nervous system disorders	Headache	19%
	Lethargy/fatigue	13%
Psychiatric disorders	Not specified	16%
Skin and subcutaneous tissue disorders	Not specified	13%

Mild and transient leukopenia and thrombocytopenia have also been reported with use of resiquimod, but these are expected only to be grade I toxicities.

Toxicities at sites of resiquimod application should be limited to grade 1, 2, or 3 (with ulceration  $\leq$  2 cm) dermatologic toxicities, and should be manageable either by continuation of resiquimod if the patient is tolerating the toxicities and if the toxicities are relatively stable, or they may be managed by holding vaccination for one to several days (up to 7 days without being a DLT).

## Adverse events expected with polyICLC (Hiltonol)

The following expected toxicities for polyICLC are based on the data from 45 patients treated with 20 mcg/kg 3x/w eek. This would be about 1.4 mg per dose and 4.2 mg per week (much higher than we will use).

Table 9: Toxicity Data for PolyICLC

Category	Toxicity	Grade	Comment		
Nervous system disorders	Headache	Grade 2	1 of 22 (<5%)		
	Tremors	Grade 3	2 of 45 (4%) poss related		
Musculoskeletal and connective tissue disorders	Muscle weakness	Grade 2	1 of 45 (<2%) experienced at Grade 3		
Respiratory, thoracic and mediastinal disorders	Dyspnea	Grade 2	1 of 45 (<2%) experienced at Grade 3		
mediastinal disorders	Нурохіа	Grade 2	1 of 45 (<2%) experienced at Grade 3		
Metabolism and nutrition disorders	Hypernatremia	Grade 2	1 of 45 (<2%) experienced at Grade 3		
	Elevated transaminases (GPT)	Grade 3	4 of 45 (9%) 3 cases possibly related; one case probably related. Typically transient.		
Investigations	Elevated Alkaline phosphatase	Grade 3	7% of patients, in IB		
	Leukocytopenia	Grade 3	2 of 45 (<4%) in published work; 20% in IB		
	Thrombocytopenia	Grade 3	14% of patients in IB		
	Neutropenia	Grade 3	10% of patients in IB		
Blood/lymph disorders	Anemia	Grade 3	13-31% of patients in IB		
General disorders and	Vaccine site reaction	Grade 2	1 of 22 (<5%)		
administration site conditions	Fever	Grade 3	14% of patients in RCC trial		
administration site conditions	Chills	Grade 3	10% of patients in RCC trial		
	Fatigue	Grade 3	10% of patients in RCC trial		

# Adverse events expected from vaccine and normal skin biopsies.

Below is a list of expected AEs related to skin biopsies:

Table 10: Toxicity Data for Skin Biopsies

Grade 2:

CTCAE Category	Description
Pain	Pain - Skin

### 7.5 Adverse Event Classifications

The determination under which adverse event classification an AE is reported. The adverse event classifications are specified in the CTCAE v4.03. For specific classifications pertaining to the protocol, we specify the following:

Version Date: 07-31-17

Hematologic/Metabolic- Any AE coded under one of the following CTCAE v4.03 categories should be reported under the Hematologic/Metabolic adverse event classification:

Table 11: Hematologic/Metabolic Classifications

Section	AE
Blood and lymphatic	Anemia Leukocytosis
Investigations	ALL EXCEPT: Carbon monoxide diffusing capacity decreased Ejection fraction decreased Forced expiratory volume decreased Vital capacity abnormal Weight gain Weight loss
Metabolism and nutrition disorders	ALL EXCEPT: Alcohol intolerance Anorexia Dehydration Glucose intolerance Iron overload Obesity Tumor lysis syndrome

Non-hematologic/Non-Metabolic- Any AE not reported under hematologic/metabolic, ocular, or allergic/autoimmune, should be reported under the non-hematologic/non-metabolic adverse event classification.

Ocular – Any AE coded under one of the following CTCAE v4.03 Adverse Event Terms should be reported under the Ocular adverse event classification:

- 1) A single treatment-related experience of the following adverse events will be classified as a DLT:
  - Eye Disorders: Night blindness (nyctalopia)
  - Eye Disorders: Papilledema
  - Eye Disordersl: Retinopathy

Participants will be referred for an ophthalmologic exam if any of these ocular adverse events occur.

- 2) A prolonged treatment-related experience (e.g., lasting > 5 days) of the following non-severe adverse events will be classified as a DLT:
  - Eye Disorders: Blurred vision
  - Eye Disorders: Flashing lights
  - Eye Disorders: Floaters

Participants will be referred for an ophthalmologic exam if any of these ocular adverse events occur.

Allergic/Autoimmune – Only AEs coded as Immune System Disorder: Allergic reaction, autoimmune disorder, or anaphylaxis should be reported under the Allergic/Autoimmune

Version Date: 07-31-17

adverse event classification. Other AEs coded under Immune System Disorder should be reported under Non-hematologic/Non-metabolic adverse event classification.

# 7.6 Reporting Adverse Events

7.6.1 Process for Reporting AEs:

## The process of reporting AEs will occur as follows:

- A. Identify the type of event using the NCI CTCAE v4.03 (Appendix 6). The CTCAE provides descriptive terminology and a grading scale for each adverse event listed.
- B. Grade the event using the NCI CTCAE v4.03.
- C. Determine whether the AE is related to the vaccine. Attribution groups are defined in Section 7.2.1.
- D. Determine the prior experience of the AE. Expected events are those that have been previously identified as resulting from administration of the vaccine. An AE is expected when it is listed in Section 7.4.3.
- E. Determine the adverse event classification of the AE, as specified and defined in Section 7.5.
- F. Determine whether the AE is a dose-limiting toxicity and report as specified below.
- G. Determine whether the AE is an SAE and report as specified below.
- H. AEs determined to require expedited reporting to the Sponsor, UVA HITC, must also be reported to your own institution according to the local policy and procedures.

## **Reporting Dose Limiting Toxicities**

All DLT's (defined in Section 7.8) should be reported by phone or fax to the HITC within 24 hours of when the site is notified of the event and entered into Oncore within 5 calendar days of when the site is notified of the event.

DLT's that are deemed serious and unexpected should be submitted to to a site's local IRB per their institutional guidelines.

### **SAE** reporting

- Report SAEs by phone or fax to the HITC within 24 hours of of when the site is notified of the event.
- Send completed FDA MedWatch 3500a form and relevant supporting documentation (e.g. clinic notes, hospital case records) to the Sponsor within 3 calendar days for deaths or life-threatening events and 5 calendar events for other SAEs.
- Enter SAE into Oncore per quidelines specified in the table below.

**DLT and SAE Reporting Information:** 

**UVA HITC** 

[contact] [contact]

[name]

In addition to DLT's and SAEs, all other AEs must be recorded into the University of Virginia Cancer Center OnCore database per the following guidelines:

Table 12: AE reporting

High Risk Studies								
Reporting requirements for AEs that occur within 30 days of the last dose of protocol specified treatm  Grade 1 Grade 2 Grade 3								nent Grade 4 & 5
	Expected and unexpected	Expected	Unexpected	Expected Unexpected  Without With Without With Hospitalization Hospitalization Hospitalization				Expected and Unexpected
Unrelated Unlikely	OnCore 30 days a	OnCore 30 days	OnCore 30 days	OnCore 30 days	OnCore 15 days	OnCore 30 days	OnCore 15 days	OnCore 7 days
Possible Probable Definite	OnCore 30 days a	OnCore 30 days	OnCore 15 days	OnCore 30 days	OnCore 15 days	OnCore 7 days	OnCore 7 days	OnCore (24-hrs)* 7 days

\*Enter into OnCore database within 24 hours if unexpected and definitely related to protocol specified treatment Hospitalization defined as an inpatient hospital stay or prolongation of a hospital stay equal to or greater than 24 hours a Grade 1 unexpected or expected hematologic/metabolic events will be recoreded in the Cancer Center Database; however, regardless of attribution, these events do not have to be reported.

## **Pregnancy**

- Report pregnancy to the Sponsor within 5 calendar days of when the site is notified of the event.
- Report the pregnancy using the Safety Reporting Cover Sheet.

Pregnancy Reporting Information:

## 7.6.2 IRB Reporting Requirements

Participating sites should follow their institutional policies for reporting adverse events and serious adverse events to their local Institutional Review Board.

The University of Virginia is responsible for reporting to the UVA IRB-HSR per the following guidelines:

Table 13: UVA IRB-HSR reporting

	•	0	
Type of Event	To whom will	Time Frame for	How reported?
	it be reported:	Reporting	
	IRB-HSR	Within 24 hours	IRB Online and phone call
resulting in death that			
is deemed			www.irb.virginia.edu/
DEFINITELY related to			_
(caused by) study			
participation			

Type of Event	To whom will	Time Frame for	How reported?
	it be reported:	Reporting	Trow reported.
(Note: An internal event is one that occurs in a subject enrolled in a UVa protocol.)			
Internal, Serious, Unexpected adverse event.	IRB-HSR	Within 7 calendar days from the time the study team received knowledge of the event.  Timeline includes submission of signed hardcopy of AE form.	IRB Online  www.irb.virginia.edu/
Unanticipated Problems that are not adverse events or protocol violations This would include a Data Breach.	IRB-HSR	Within 7 calendar days from the time the study team received knowledge of the event.	Unanticipated Problem report form.  http://www.virginia.edu/vprg_s/irb/HSR_docs/Forms/Rep_orting_Requirements-Unanticipated_Problems.doc_)
Protocol Violations (The IRB-HSR only requires that MAJOR violation be reported, unless otherwise required by your sponsor, if applicable.) Or Enrollment Exceptions	IRB-HSR	Within 7 calendar days from the time the study team received knowledge of the event.	Protocol Violation and Enrollment Exception Reporting Form  http://www.virginia.edu/vpr/irb/hsr/
Data Breach	The UVa Corporate Compliance and Privacy Office and	As soon as possible and no later than 24 hours from the time the incident is identified.	UVa Corporate Compliance and Privacy Office- [contact]
	ITC: if breach involves electronic data-	As soon as possible and no later than 24 hours from the time the incident is identified.	ITC: Information Security Incident Reporting procedure, http://www.itc.virginia.edu/s ecurity/reporting.html
	UVa Police if breach includes such things as stolen computers.	IMMEDIATELY.	Phone- [contact]

Version Date: 07-31-17

# 7.6.3 Additional Reporting Requirements for the Sponsor (UVA)

## Reporting to the FDA

Serious and unexpected suspected adverse reactions will be reported to the FDA no later than 15 calendar days after the sponsor determines that the requirements for an IND safety report have been met. The FDA will be notified using an FDA Form 3500a.

Unexpected fatal or life-threatening suspected adverse reactions will be reported to the FDA no later than 7 calendar days after the Sponsor receives the initial information of the event. The FDA will be notified using an FDA Form 3500a.

Other adverse event information will be sent to the FDA in the IND annual report.

## Reporting to the Sites

The sponsor will report serious and unexpected suspected adverse reactions to the outside sites no later than 15 calendar days after the sponsor determines that the requirements for an IND safety report have been met.

7.6.4 Reporting of Subject Withdraw als/Dropouts Prior to Study Completion Subjects who withdraw consent and those dropping out of the study secondary to an AE will be reported to the UVA IRB yearly on the IRB continuation form. These data should be reported to the sponsor within 30 days of subject withdrawal or dropout.

## 7.7 Adverse Event Review and Monitoring

7.7.1 In addition to clinic notes, adverse events will be initially captured using study-specific tools and participant toxicity diaries.

As specified in the study flow chart (Appendix 1), each participant will be evaluated by a licensed clinician. The following will be performed as designated in the protocol: routine disease-directed physical exam including performance status, blood collection, reassessment for vitiligo, and examination of the skin and nodal basins for evidence of metastasis.

Participants will keep a daily diary of toxicities for days 1 through 85. The diaries will be reviewed by a research clinician prior to the next scheduled vaccine. During clinic visits, participants will also be asked about subjective symptoms including headache, malaise, fatigue, dyspnea, nausea, rash, diarrhea, abdominal discomfort, peripheral nerve pain, visual changes, appetite, tremors, night sweats, and ability to concentrate. Additional toxicities will be captured from laboratory tests. For each AE (with the exception of Grade 1 hematologic/metabolic events), date of onset, duration, grade, and attribution will be noted in the participant's study chart, on study documents, or in the clinic note, and will be entered into the UVA Cancer Center database.

After each vaccination, participants will be observed for AEs for at least 20 minutes. Follow-up phone calls will be made per the judgment of the research clinicians with regard to individual participant need. Subjects will be instructed on how to reach their provider should they have any questions and/or problems during the study.

In the event of an AE, appropriate action will be taken to ensure adequate care for the participant. If the participant is still on protocol, treatment delay or withdrawal from the protocol will be considered according to the protocol guidelines.

Version Date: 07-31-17

- 7.7.2 Individual AEs will be reviewed at each site by the Principal Investigator, nurse practitioner(s), and clinical research coordinator(s) (CRC),.
- 7.7.3 SAEs experienced by participants at all sites will be reviewed twice a month by the sponsor during the UVA Melanoma Team meeting. This meeting will occur at least 20 times in a calendar year. Those present at the meeting include the sponsor/overall study Pl, subinvestigators, protocol development staff, biostatisticians, research nurses, research coordinators, laboratory specialists, and laboratory research managers. These meetings may also include the review of individual participants to assess whether they are protocol candidates, whether AEs warrant discontinuation, and whether existing protocols should be continued or closed.
- 7.7.4 Monthly conference calls will be held with the Sponsor and the site designee to review protocol status, accruals, and adverse events.
- 7.7.5 The following laboratory values will be recorded in the UVA Cancer Center database, graded using the CTCAE v4.03 (if a grading category exists), and reported as described in Section 7.6:
  - 1. Alk Phosphatase
  - 2. ALT (GPT)
  - 3. ANA
  - 4. AST (GOT)
  - 5. Bilirubin, total
  - 6. Creatinine
  - 7. Eosinophil #
  - 8. Hepatitis C serology
  - 9. beta-HCG
  - 10. HqB
  - 11. HIV
  - 12. HLA type
  - 13. LDH
  - 14. Potassium
  - 15. RF
  - 16. Urinalysis
  - 17. WBC

Any abnormal laboratory values captured which are not included in the above list, but are considered to be pertinent positive clinical signs/symptoms, and laboratory results obtained as part of routine care of patients will be recorded in the UVA Cancer Center database and reported as described in Section 7.6. If there is any doubt on the part of study personnel concerning what constitutes a pertinent positive finding, the sponsor is to be consulted.

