# 4.4.3 Management of Participants

This study will be conducted on an outpatient basis, with participants scheduled to be evaluated on days 1, 8, 15, 22, 36, 43, 57, 78, and 85, and week 26 (or more often if needed for testing or medical reasons). As needed, there may also be follow-up within 1-3 weeks after biopsies performed on days 8 or 22 for wound evaluation. Participants will also be followed-up at 52 weeks (1 year) and at 2 years with blood draws for studies of immune response durability. During off treatment follow-up, participants will be followed yearly for survival and disease status.

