# 5.5.4 Delayed Visit for Reasons Other Than Toxicity

A schedule for return visits should be established at the first visit. If a participant misses a treatment, the missed treatment will be administered as soon as possible, so that the subsequent vaccinations are given in the appropriate intervals. Treatment may be continued for an additional time period, if needed. Participants who are vaccinated outside of the established schedule should return to the original schedule as soon as possible.

The table below defines what constitutes a delayed visit, whether the participant should continue to be treated, and whether a protocol violation/deviation should be reported and recorded. The range of days is counted from the original scheduled date.

Table 6. Delayed Visit for Reasons other than Toxicity				
Treatment Period	Range of Days	Participant Treatment	Protocol Deviation	
Vaccine 1				
Day 1	± 2 days	Vaccine/Labs	No	
	± 3 to 7 days	Vaccine/Labs	Yes	
	± 8 or more days	Labs	Yes	
Vaccine 2/Biopsy*				
Day 8	± 2 days	Vaccine/Labs/Biopsy	No	
	± 3 to 7 days	Vaccine/Labs/Biopsy	Yes	
	± 8 or more days	Labs	Yes	
Vaccine 3*				
Day 15	± 2 days	Vaccine/Labs	No	
	± 3 to 7 days	Vaccine/Labs	Yes	

	± 8 or more days	Labs	Yes
Assessment/Biopsy			
Day 22	± 2 days	Biopsy/Labs	No
	± 3 to 7 days	Biopsy/Labs	Yes
	± 8 or more days	Labs	Yes
Assessment			
Day 43	L O dovo	Labs	No
	± 2 days	1 1 1	
	± 3 to 7 days	Labs	Yes
	± 8 or more days	Labs	Yes
Vaccines 4-6*			
Days 36, 57, 78	± 7 days	Vaccine/Labs	No
	± 8 to 14 days	Vaccine/Labs	Yes
	± 15 or more days	Labs	Yes
Assessment			
Day 85 (Week 12)	± 7 days	Labs/Scans	No
	± 8 to 14 days	Labs/Scans	Yes
	± 15 or more days	Labs	Yes
Follow-up			
Week 26, Year 1 and 2	± 7 days	Scans/Labs	No
	± 8 to 30 days	Scans/Labs	Yes

A participant will be taken off protocol treatment if more than one vaccination is delayed [ $\pm$  3 to 7 days] during the treatment period.

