- Review of participant diary and distribute new toxicity diary
- Medication review
- Vaccine administration

# 6.2.8 Day 78

- Interval history and physical examination directed at new signs and symptoms. Examination of the vaccine site(s) should be included.
- Vital signs
- Weight
- Performance status
- Review of adverse events
- CBC with differential, including automated lymphocyte count if available (0.3 ml)
- Comprehensive chemistry panel to include sodium, potassium, creatinine, glucose, calcium, total bilirubin, AST, ALT, and alkaline phosphatase. (0.9 ml)
- Lactate Dehydrogenase (LDH) (0.3 ml)
- Anti-nuclear antibody and rheumatoid factor (4 ml total)
- Review of participant diary and distribute new toxicity diary
- Medication review
- Vaccine administration

## 6.2.9 Day 85

- Interval history and physical examination directed at new signs and symptoms. Examination of the vaccine site(s) should be included.
- Vital signs
- Weight
- Performance status
- Review of adverse events
- CBC with differential, including automated lymphocyte count if available (0.3 ml)
- Comprehensive chemistry panel to include sodium, potassium, creatinine, glucose, calcium, total bilirubin, AST, ALT, and alkaline phosphatase. (0.9 ml)
- Lactate Dehydrogenase (LDH) (0.3 ml)
- Chest X-ray or chest CT
- Visual acuity exam using a Snellen chart, and color vision exam using an Ishihara eye chart
- Neurologic function
- Note hair and eye color
- Assessment of skin for vitiligo
- Review of participant diary
- Medication review
- Blood collection for immunologic testing:\_The following blood samples for research will be provided to UVA and processed by the UVA BTRF and stored by the UVA-HITC IML:
  - 80 cc blood collected in heparinized green top tubes for lymphocytes.
  - o 20 cc blood collected in red top tubes for serum

### 6.2.10 Week 26

 Interval history and physical examination directed at new signs and symptoms. Examination of the vaccine site(s) should be included.

Version Date: 07-31-17

- Vital signs
- Weight
- Performance status
- Anti-nuclear antibody and rheumatoid factor (4 ml total)
- Chest x-ray or chest CT
- Neurologic function
- Assessment of skin for vitiligo
- Medication review
- Blood collection for immunologic testing:\_The following blood samples for research will be provided to UVA and processed by the UVA BTRF and stored by the UVA-HITC IML:
  - o 80 cc blood collected in heparinized green top tubes for lymphocytes.

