# 7.4.2 Time Span for Reporting Adverse Events

Reporting of AEs will begin when the subject is administered the study drug or has a study related biopsy. Events occurring through 30 days after administration of the last vaccine, regardless of attribution, will be reported. AEs should be followed to resolution or stabilization. If an AE worsens and becomes an SAE, it should be reported as serious per the guidelines specified for SAE reporting.

AEs that are possibly, probably, or definitely related to the vaccine will be recorded until the subject completes treatment follow-up. If, during treatment follow-up, the subject receives additional treatment, subjects will be off treatment follow-up and will be followed yearly for disease progression and survival.

7.4.3 Agent-Specific Expected Adverse Events List: Any AE not on this list will be considered an unexpected AE.

Expected toxicities related to peptide vaccines. This list of expected AEs for the LPV7 vaccine is based on prior data from the UVA-Mel 44 clinical trial in which 41 participants in Arm A received a mixture of 12 Class I peptides plus a tetanus helper peptide in an emulsion with Montanide ISA-51 adjuvant. AEs are listed only if observed in  $\geq$  5% of treated participants.

Table 7: Summary Toxicity Data from UVA-Me44 Grade 2:

CTCAE Category	Description		
Investigations	Lymphocyte count decreased		
General disorders and administration site conditions	Fatigue		
General disorders and administration site conditions	Fever		
Skin and subcutaneous tissue disorders	Hyperhidrosis		
Skin and subcutaneous tissue disorders	Skin induration		
Skin and subcutaneous tissue disorders	Skin ulceration		
General disorders and administration site conditions	Injection site reaction		
Gastrointestinal Disorders	Nausea		
Metabolism and nutrition disorders	Hyperglycemia		
General disorders and administration site conditions	Flu-like symptoms		
Skin and subcutaneous disorders	Other: any rash		

\*NOTE: Hyperglycemia  $\geq$  Grade 3 is not an expected event. If a non-fasting hyperglycemia adverse event occurs at a level  $\geq$  Grade 3, a fasting serum glucose test will be ordered and the event will be re-graded appropriately. The fasting serum glucose measurement will be used for the purpose of determining reporting requirements.

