# 10.0 Appendices

# 10.1 Appendix 1: X-page

						Activ	Trea	tment				I	Follow-u	Jp qı
01 - Harris 0 Tarata	Day	Pre	1	8	15	22	36	43	57	78	85	183	365	730
Studies & Tests	Week		0	1	2	3	5	6	8	11	12	26	52	104
	Vax #		1	2	3		4		5	6				
Informed consent a		Х												
Class I HLA-typing a		Х												
Pathology review a		Χ												
β-HCG °		Χ												
HIV / Hepatitis C d		Х												
HGBA1C b		Х												
Urinalysis b		Х												
CBC with differential b		Х				Х				Х	Х			
Comprehensive chemistry b, f		Xe				Х				Х	Х			
LDH b		Х				Х				Χ	Х			
Anti-nuclear antibody / Rf factor			Х			Х				Х		Х		
Chest x-ray / CT b, g		Х									Х	Х		
Abdominal CT b, g		Χ												
Pelvic CT b, g		Х												
Head MRI / CT b, g		Х												
History & physical b		Χ	Х	Х	Х	Х	Χ	Χ	Χ	Χ	Х	Х	Х	Х
120cc green top tubes			Х											
80cc green top tubes				Х		Х		Х			Х	Х	Х	Х
20cc red top tubes			Х	Х		Х		Χ			Х	Х	Х	Х
Vaccination			Х	Х	X		Х		Х	Χ				
Biopsynormal skin, pts 1-6, in Part 1				Χi		Χ i								
Vaccine Site Biopsies				Х		Х								
Visual acuity, and color acuity examinations			Х								Х			
Note hair and eye color			Х								Х			
Note vitiligo			Х			Х					Х	Х		
Note neurologic function			Х			Х					Х	Х		
Distribute/review participant toxicity diary			Х	Х	Х	Х	Х	Х	Х	Х	X h			

<sup>a Any point prior to randomization

b Pre-study within 6 weeks of randomization

<sup>c Within 2 weeks of randomization (for childbearing women)

d Within 6 months of randomization

e To include fasting glucose. Fasting blood sugars may be evaluated 4h or more after last eating.

f Comprehensive chemistry panel to include sodium, potassium, creatinine, glucose, calcium, total bilirubin, AST, ALT, and alkaline phosphatase

PET-CT may replace CT of the chest, abdomen, and/or pelv is. New abnormalities of AST, ALT, or LDH levels, or new nodules on CXR will warrant more complete staging with CT scans of the chest, abdomen and pelv is or PET-CT and with CT or MRI of the brain as appropriate.

h Review only

Biopsies of normal skin to be done just for the first 6 patients enrolled in Part 1.

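### Days 86 to 108 have no diary and no scheduled contact, although all adverse events must be reported through 30 days after the last vaccine

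*Combined protocol and SAP*

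**What the plan says.** **What must be reported.** Section 7.4.2 sets two duties. The first covers any cause: "Events occurring through 30 days after administration of the last vaccine, regardless of attribution, will be reported". The second covers related events for longer: "AEs that are possibly, probably, or definitely related to the vaccine will be recorded until the subject completes treatment follow-up". Table 12 uses the same 30-day limit. Section 7.7.1 asks for onset date, duration, grade and attribution for each AE other than grade 1 hematologic/metabolic events.

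**What is collected.** Section 7.7.1: "Participants will keep a daily diary of toxicities for days 1 through 85". The X-page row "Distribute/review participant toxicity diary" ends at day 85, where a footnote limits it to review, so no new diary is handed out. Under section 4.4.3 participants are "evaluated on days 1, 8, 15, 22, 36, 43, 57, 78, and 85, and week 26 (or more often if needed"; the parenthesis goes on to name testing or medical reasons. The X-page puts week 26 at day 183. In section 6.2 the item "Review of adverse events" appears at every visit from day 8 to day 85, and is absent from 6.2.10 (week 26) and 6.2.11 (weeks 52 and 104). Telephone calls are left to clinical judgment (7.7.1).

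**Visit windows.** On Table 6, section 5.5.4 says: "The range of days is counted from the original scheduled date". Vaccine 6 (day 78) and the day-85 assessment may each move by up to 7 days without a deviation.

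**The concern.** The reporting duty runs longer than the tools that feed it. After day 85 the 30-day window stays open, but nothing planned asks the participant about AEs until about 11 weeks after it has closed. The longer duty to record related AEs falls on visits whose task lists do not include AE review.

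This matters most for Part 2. Its first objective is the safety of six vaccines given at one skin site, and the days after vaccine 6 carry the greatest cumulative exposure there. The same data feed the DLT count that Table 21 monitors, where the boundaries are 2, 3 and 4 DLTs. With numbers that small, one late or missed DLT can decide whether accrual is paused for review.

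**Working it through.** The documents give no figure on this point to reproduce; the check is day arithmetic on the schedule.

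**Inputs.** Vaccine 6 on day 78 (Table 6, X-page). Reporting window 30 days after the last vaccine (7.4.2). Diary ends on day 85 (7.7.1). Next visit on day 183 (X-page). No-deviation windows of ±7 days for vaccine 6 and for the day-85 assessment (Table 6). Part 2 accrual of 2 per month and a maximum of 18 (9.5.2).

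**Step 1, nominal schedule.**
- The window closes on day 78 + 30 = day 108.
- The diary covers days 79 to 85, which is 85 − 78 = 7 of the 30 days.
- Uncovered: 108 − 85 = 23 days, and 23/30 = 77%.
- The next visit is 183 − 85 = 98 days after the last one, and 183 − 108 = 75 days after the window closes.

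**Step 2, vaccine 6 moved within the no-deviation window.**

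| Vaccine 6 given | Window closes | Window days after day 85 | Window close to day 183 |
|---|---|---|---|
| Day 71 (−7) | Day 101 | 16 of 30 | 82 days |
| Day 78 | Day 108 | 23 of 30 | 75 days |
| Day 85 (+7) | Day 115 | 30 of 30 | 68 days |

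In the last row the day-85 assessment can take place on the day of the injection with no deviation. The last listed AE review, safety laboratory tests and vision test would then have no follow-up time after vaccine 6.

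**Step 3, sensitivity to how the diary is read.** Steps 1 and 2 take day 85 literally. Suppose instead that sites let the diary run to the assessment visit, and that visit is held on day 92, the latest date without a deviation. Coverage is then 92 − 78 = 14 of 30 days on schedule (16 uncovered), or 92 − 85 = 7 of 30 if vaccine 6 was given on day 85 (23 uncovered). The gap narrows but does not close.

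**Step 4, delay for monitoring.** An event starting on days 86 to 108 and first elicited on day 183 is known 75 days (183 − 108) to 97 days (183 − 86) after onset. At 2 participants a month, with 30-day months, 75/30 × 2 = 5 and 97/30 × 2 = 6.5. So about 5 to 6 of the planned 18 could enrol in the meantime. This assumes no spontaneous report and accrual still open.

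**Step 5, which events could be missed.** Sections 7.5 and 7.8 include DLTs that can come and go inside the gap: treatment-related blurred vision, flashing lights or floaters lasting more than 5 days, and unexpected related allergic or autoimmune reactions of grade 2 or higher. Vision is last tested at the day-85 visit.

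**The case against.** The strongest reply is that follow-up is not silent. The visits at weeks 26, 52 and 104 each require an interval history and an examination for new signs or symptoms, and section 6.2 adds at each: "Examination of the vaccine site(s) should be included". Section 7.7.1 has participants asked about a list of symptoms at clinic visits, with no limit at day 85. Week 26 also includes neurologic, vitiligo, ANA/rheumatoid factor and chest imaging checks. AEs already present at day 85 must be followed until they resolve or stabilize (7.4.2). Participants are told to report events at any time (5.4.5), and extra visits are allowed when needed.

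All of this stands, and it rules out a stronger conclusion that a reader might draw: that late same-site events go largely unsolicited. The vaccine site is expressly examined at every follow-up visit, and induration, which section 5.4.2 says may last for months, is likely to be seen at day 85 or week 26.

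Two further inferences go beyond the documents.
- **That the gap biases Arm E2 against Part 1 Arm E, or shifts Table 21 by a known amount.** Both parts share the schedule, so the gap alone does not produce a difference between them. A DLT must be unexpected and related, grade 2 site reactions are on the expected list, and participants are likely to report severe ulceration themselves. No missed-event rate is given.
- **That the closing visit could come a week before vaccine 6.** Table 6 permits it formally (day 78 against day 85), but the X-page puts vaccine 6 at week 11 and that visit at week 12. The same-day case is the realistic one.

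What the reply does not reach is the interval itself. No scheduled visit falls between days 85 and 183, so an event that starts and resolves there depends on spontaneous report or later recall.

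**Conclusion.** The point holds as a mismatch between the reporting duty and the collection schedule. On the nominal schedule 23 of the 30 days on which every AE is reportable have no diary and no scheduled contact. With vaccine 6 on day 85, no diary day remains, and there is no scheduled contact either if the day-85 assessment keeps its date. The AE-review item is also missing from the three follow-up visits at which related AEs should still be recorded.

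The events at risk are new ones that begin after day 85 and resolve before day 183, together with their onset dates and peak grades. Any error runs towards under-counting late AEs and DLTs. Its size cannot be estimated from the documents, and no sample size or error rate changes.

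This rests on two readings: that the diary ends on day 85 as written (step 3 gives the alternative), and that weeks 26, 52 and 104 belong to treatment follow-up for participants who start no other therapy. Section 7.4.2 gives no day for the end of that follow-up; the X-page lists those visits under follow-up. The change is worth making because safety is a primary endpoint and the change is cheap.

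**What to change.** 1. In 7.7.1, 6.2.9 and the X-page, issue a diary at the day-85 visit and continue it through 30 days after the last vaccine actually given. Have it returned by mail or electronically when the window closes, so that any DLT reaches the Table 21 monitoring promptly. Reviewing it only at week 26 would be too late for that purpose.
2. Add "Review of adverse events" to 6.2.10 and 6.2.11.
3. When comparing E2 with Part 1 Arm E, also tabulate AEs to day 85 only, so that longer collection does not itself create a difference.
4. Reconcile the Table 6 windows for vaccine 6 and the day-85 assessment, which allow both on one day without a deviation, with the order on the X-page (week 11, then week 12). Which should give way is for the sponsor to decide; moving the assessment would also move the week-12 blood draw used for peak immune response (9.7.2).

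**Cost.** Items 1 to 3 need protocol wording, one more diary form with its review, and two lines in the visit lists, with no new visit or test. Participants on schedule keep the diary for 23 more days. E2 will record slightly more AEs than Part 1's collection would have, which the day-85 tabulation handles.
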